**Table 1: Schedule of Activities for Screening and 26-Week Treatment Period**

Period	Screening	Treatment Period													Notes
Visit		1	2	3	4	5	6	7	8	9	10	11	12	13	
Week	Up to 2 W		W1	W2	W3	W4	W6	W8	W10	W12	W14	W18	W22	W26/ED a	
Days and Window	D -14 to -1	D1	D8 ± 2	D15 ± 2	D22 ± 2	D29 ± 2	D43 ± 2	D57 ± 2	D71 ± 3	D85 ± 3	D99 ± 3	D127 ± 3	D155 ± 3	D183 ± 3	
Blood and urine samples for RTCA		X h	X		X			X		X		X		X	All sites are to collect and ship frozen RTCA plasma and urine samples to the central laboratory. Only selected sites will perform additional on-site testing of freshly collected blood, plasma and urine using a dedicated RTCA reader and specific instructions provided by the Sponsor and as defined in the laboratory manual. See Section 8.9.3
Blood sample for genetic testing i		X i													May be collected anytime during study
Study Intervention															
Randomization		X													
Ravulizumab or placebo		X		X					X			X			Administer after all other required tests/procedures.

Note: All assessments should be performed prior to administration of study drug on dosing days, unless otherwise specified. For participants on dialysis, study visits should be conducted on non-dialysis days, whenever possible. However, if this is not feasible, then all study-related procedures and study drug administration should be performed prior to the participant receiving dialysis.

a For participants who discontinue study drug prior to the end of the Treatment Period, the ED visit should be completed as soon as possible. In addition, a Follow-up Phone Call will be performed 8 weeks (56 days) ± 5 days following the participant's last dose of study drug to collect concomitant medications, nonpharmacologic therapies and procedures, and AEs.

b Weight should be obtained at every visit and measured predose on dosing visits. The dose regimen is based on the last recorded study visit body weight. If the study drug is prepared the day before a visit, the weight from the previous study visit may be used.

c Vital sign measurements include systolic and diastolic BP, pulse oximetry, heart rate, respiratory rate, and body temperature. On dosing days, vital signs will be taken predose.

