4.3. Changes from Analyses Specified in the Previous Version of the SAP

Abbreviations: FACIT = Functional Assessment of Chronic Illness Therapy; PA2 = Protocol Amendment 2; SAP = statistical analysis plan; TMA = thrombotic microangiopathy

5. **DEFINITIONS**

5.1. **Primary Endpoint**

The primary efficacy endpoint of the study is complete TMA response during the 26-week randomized Treatment Period.

Complete TMA response is defined as normalization of hematologic parameters (platelet count and LDH) and \geq 30% improvement in estimated glomerular filtration rate (eGFR) from Baseline (Table 2).

Table 2:	Overview of Complete Thromb	ootic Microangiopathy Response
----------	------------------------------------	--------------------------------

		TMA Response Parameter
Complete TMA response	Hematologic response	 Normalization of platelet count (defined as platelet count ≥ 150000/µL) without transfusion support during the prior 7 days Normalization of LDH (defined as LDH
		\leq 1.5 × upper limit of normal)
	Renal response	• Improvement in eGFR of ≥ 30% compared to Baseline

Abbreviations: eGFR = estimated glomerular filtration rate; LDH = lactate dehydrogenase; TMA = thrombotic microangiopathy

If a participant is not on dialysis at Baseline, baseline eGFR will be defined as the last nonmissing assessment value prior to the start of study treatment. If a participant is on dialysis at Day 1, baseline eGFR will be set to 10 mL/min/1.73 m². If a participant is on dialysis during the entire 26-week randomized Treatment Period or through early discontinuation of study drug, then the change in eGFR will not be calculated.

For complete TMA response, participants must have met all 3 TMA response parameters simultaneously, with each component meeting the requirement at 2 separate assessments obtained at least 24 hours apart, and any measurement in between. The first laboratory value will be assessed based on central laboratory results; the second laboratory value will be assessed based on the earliest value obtained \geq 24 hours after the first value and may be based on central or local laboratory results.

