9.3.10. Serum Creatinine and eGFR

Serum creatinine measurements are not reliable with concurrent dialysis. Therefore, all serum creatinine values obtained while a participant is on dialysis will be excluded from all analyses. The eGFR rate will be imputed with a value of 10 (in mL/min/1.73 m²) while a participant is on dialysis. A participant will be considered on dialysis from the first day of dialysis through 5 days after the end of dialysis. A participant will be considered as not requiring dialysis at a specific post-Baseline time point if they have been dialysis free for at least 14 days prior to that time point. This rule will only be applied to postbaseline assessments of serum creatinine and eGFR.

The eGFR will be calculated based on creatinine using CKD-Epi equation in patients \geq 18 years of age:

eGFR = $141 \times \min(SCr/\kappa, 1)\alpha \times \max(SCr/\kappa, 1)-1.209 \times 0.993$ Age x 1.018 [if female] × 1.159 [if Black]

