9.3.11. Platelets and Hemoglobin

Platelet and hemoglobin measurements are not reliable with concurrent red blood cell (RBC) and/or platelet transfusions. Therefore, platelet values obtained on the day of a blood transfusion of platelets through 7 days after the transfusion will be excluded from all analyses. Hemoglobin values obtained on the day of a blood transfusion of either whole blood or packed RBCs through 7 days after the transfusion will be excluded from all analyses. This rule will only be applied to postbaseline assessments of platelets and hemoglobin.

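### Baseline eGFR has no post-dialysis washout, so a participant whose dialysis ended just before Day 1 faces a renal-response threshold set too high

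*SAP*

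**What the plan says.** The SAP handles dialysis and eGFR in two places.

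After baseline, SAP 9.3.10 gives the reason for its rule, "Serum creatinine measurements are not reliable with concurrent dialysis", and the window, "A participant will be considered on dialysis from the first day of dialysis through 5 days after the end of dialysis". Creatinine from that window is dropped and eGFR is imputed as 10 mL/min/1.73 m². The paragraph ends by limiting its own scope: "This rule will only be applied to postbaseline assessments of serum creatinine and eGFR".

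At baseline, SAP 5.1 has two branches: "If a participant is on dialysis at Day 1, baseline eGFR will be set to 10" (same units), and "If a participant is not on dialysis at Baseline, baseline eGFR will be defined as the last nonmissing assessment value prior to the start" (that is, before the first dose). SAP 9.3.1 confirms that the eGFR baseline is governed by 5.1 alone. One branch refers to dialysis at Day 1 and the other to dialysis at Baseline. Neither state is defined, and no interval is required between the end of dialysis and the baseline creatinine. Protocol 9.4.1.1 leaves the baseline imputation to the SAP.

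Renal response is an eGFR at least 30% above baseline. It is one of the three parameters that must all be met for Complete TMA Response, the primary endpoint. Change from baseline in eGFR is a secondary endpoint.

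**The concern.** Dialysis removes creatinine, so a sample taken soon afterwards overstates kidney function. The SAP accepts this for every later visit and discards such values for 5 days. At baseline, the value from which every later eGFR is judged, the same protection is absent for anyone who is no longer on dialysis at Day 1.

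Such participants can be enrolled. Inclusion criterion 5c admits new dialysis due to TMA of more than one session, begun no more than 14 days before Screening, and Screening may last 2 weeks. A short course can therefore start and finish before Day 1.

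The error runs one way within a participant. A baseline eGFR that is too high raises the response threshold and understates the change from baseline. A real recovery can be recorded as nonresponse, against a creatinine that the SAP would have thrown away one visit later.

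**Working it through.** The plan gives no figure for the effect of this rule, so there is none to reproduce. The sample-size statement does not bear on it.

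**Who is affected.** Following the text for each dialysis history:

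- *Dialysis course continuing at Day 1:* SAP 5.1 sets baseline to 10. Not affected.
- *Course ended 1 to 5 days before Day 1:* not on dialysis at Day 1 in the ordinary sense, so the last observed value is used. The same sample after baseline would be replaced by 10. Affected.
- *Last nonmissing value drawn during Screening dialysis that ended before Day 1 (for example, if the Day 1 creatinine is missing):* the observed value is used. Affected.
- *Course ended more than 5 days before the baseline sample:* the observed value would also be accepted after baseline. No inconsistency.

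**How far the threshold moves.** Inputs: the creatinine exponent −1.209 from the CKD-EPI equation in SAP 9.3.10, and the 30% criterion from SAP 5.1. Assumption: creatinine lies above the equation's constant κ with and without the dialysis effect. Then eGFR is proportional to creatinine^(−1.209), and κ, age, sex and race cancel within a participant.

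Let f be the fraction by which dialysis has lowered the baseline creatinine. The documents do not give f, so a range is assumed.

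- Inflation of baseline eGFR: (1 − f)^(−1.209)
- True improvement needed for renal response: 1.3 × (1 − f)^(−1.209) − 1

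| Assumed f | Inflation factor | True improvement needed | Recorded baseline if the true value is 10 (assumed) | Threshold |
|---|---|---|---|---|
| 0% | 1.000 | 30% | 10.0 | 13.0 |
| 10% | 1.136 | 1.3 × 1.136 − 1 = 48% | 11.4 | 14.8 |
| 20% | 1.310 | 1.3 × 1.310 − 1 = 70% | 13.1 | 17.0 |
| 30% | 1.539 | 1.3 × 1.539 − 1 = 100% | 15.4 | 20.0 |

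Setting (1 − f)^(−1.209) = 1.3 gives f = 1 − 1.3^(−1/1.209) = 0.195. A dialysis effect of about 20% on creatinine is therefore enough to cancel a full 30% recovery. In the same illustration, change from baseline in eGFR is understated by 1.4, 3.1 or 5.4 mL/min/1.73 m² (recorded baseline minus 10).

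**What one participant is worth.** SAP Section 4 reports 16 enrolled, randomized 1:1. With an assumed 8 per arm, one misclassified participant moves that arm's response rate by 1/8 = 12.5 percentage points.

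**The case against.** The strongest reply is that the text can be read so that no gap exists. The 5-day sentence is the SAP's only definition of being on dialysis. If the closing limit covers only the 14-day sentence just before it, the definition could carry over to Day 1 in 5.1. This is possible but not the natural reading. The 14-day sentence already restricts itself to times after baseline, and SAP 9.3.11 closes its whole exclusion rule with the parallel line "This rule will only be applied to postbaseline assessments of platelets and hemoglobin". Under either reading the SAP needs to say which applies.

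A second reply stands. A baseline of 10 is a placeholder, not the true value of someone who has come off dialysis, and its threshold of 13 may credit recovery that preceded study drug. The SAP already accepts this cost for participants on dialysis at Day 1, but it is a cost.

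A reader might also infer more than the documents support:

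- *That anyone with a session in the 5 days before Day 1 is affected.* A participant between sessions of a continuing course is on dialysis at Day 1 and gets 10. The Table 1 note, "For participants on dialysis, study visits should be conducted on non-dialysis days, whenever possible", uses the term for a status, not a same-day session, and 9.3.10 counts from the end of dialysis, not from each session.
- *That the proportion on dialysis at presentation, cited in Protocol 4.2.2, sizes the problem.* It includes those still on dialysis at Day 1, who are already set to 10. The share who stopped shortly before is not reported.
- *That the distance between an observed-value threshold and 13 is the bias.* It is the distance between two rules. The bias depends on f, which is unknown.
- *That one arm is favored.* The rule is identical in both arms and randomization was stratified by baseline dialysis status.
- *That the parallel hemoglobin rule in 9.3.11 also harms the primary endpoint.* Hemoglobin is not a component of Complete TMA Response.

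**Conclusion.** The concern holds for a limited group: participants whose dialysis course ended within 5 days before the baseline creatinine sample, or whose last value was drawn during Screening dialysis that ended before Day 1. As written, the SAP gives them a baseline that it would reject as unreliable at any later visit. For an assumed 10% to 30% lowering of creatinine, the true improvement needed rises from 30% to between 48% and 100%.

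The number of such participants is not in the documents and could be zero. The expected effect is some missed renal responses and understated eGFR change in either arm, not a tilt toward one treatment. SAP 4.2 removes hypothesis tests for treatment comparison, so the consequence falls on the descriptive rates, their 95% confidence intervals (SAP 7.3.1) and the eGFR summaries. With so few participants, a single one matters there. It is an inconsistency in the primary-endpoint derivation that should be corrected before analysis, but it does not undermine the trial.

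**What to change.** In SAP 5.1, define on-dialysis status at Day 1 with the 9.3.10 window: from the first day of dialysis through 5 days after its end, judged at the date of the baseline creatinine sample. Participants inside that window then also receive a baseline eGFR of 10. Use the same term in both branches of 5.1, and reword the last sentence of 9.3.10 so that it does not contradict this.

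List the participants whose baseline changes. Repeat Complete TMA Response and change from baseline in eGFR with their observed baseline as a sensitivity analysis. This is needed because the threshold of 13 may count some pretreatment recovery as response. If the two versions agree, the choice does not matter.

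The cost is small: a short definition, a listing and one repeated summary. Protocol 8.2.2 has dialysis status before and during Screening recorded on the CRF. It does not say in terms that end dates are recorded for dialysis before Day 1, so confirm this first. Settle the definition before treatment assignments are known to those preparing the analysis.

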#### Disease Characteristics

4. TMA within  $\leq$  14 days prior to Screening is associated with at least 1 of the following triggers:
  - a. Autoimmune (lupus nephritis, systemic sclerosis associated TMA [SSc-TMA])
  - b. Infection
  - c. Solid organ transplant (eg, kidney, pancreas, liver, heart, small bowel)
  - d. Drugs
  - e. Malignant hypertension

5. Confirmation of all of the following laboratory findings during the Screening Period and/or  $\leq 14$  days prior to the start of the Screening Period:
  - a. Platelet count  $< 150,000/\mu\text{L}$
  - b. Lactate dehydrogenase  $\geq 1.5 \times \text{ULN}$  and hemoglobin  $\leq \text{LLN}$  (based on age and sex)
  - c. Acute kidney injury as defined by meeting 1 or more of the following criteria (for kidney transplant recipients, the pre-TMA value is based on post-transplant eGFR):
    - Acute decline in eGFR  $\geq 50\%$  from pre-TMA value (pre-TMA value must be  $\leq 12$  months prior to Screening)
    - New acute kidney injury with an eGFR  $\leq 30 \text{ mL/min}/1.73 \text{ m}^2$
    - New initiation of dialysis due to TMA requiring  $> 1$  session and for no more than 14 days prior to Screening

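### The 5-day post-dialysis rule for creatinine is not applied to baseline eGFR, so the 30% response threshold may be too high for participants who stopped dialysis shortly before the baseline sample

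*SAP*

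**What the plan says.** SAP 9.3.10 starts from the premise that "Serum creatinine measurements are not reliable with concurrent dialysis". It excludes creatinine values obtained on dialysis, imputes eGFR as 10 mL/min/1.73 m² for that time, and sets the window: "A participant will be considered on dialysis from the first day of dialysis through 5 days after the end of dialysis". It then limits the scope: "This rule will only be applied to postbaseline assessments of serum creatinine and eGFR".

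Baseline eGFR is defined in SAP 5.1, and SAP 9.3.1 refers back to that section. There are two branches. For a participant not on dialysis at Baseline, "baseline eGFR will be defined as the last nonmissing assessment value prior to the start of study treatment". The other branch reads "If a participant is on dialysis at Day 1, baseline eGFR will be set to 10" (mL/min/1.73 m²). Neither branch mentions days since the last dialysis. Protocol 9.4.1.1 has the same two branches and leaves the imputation to the SAP.

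The renal component of Complete TMA Response in SAP 5.1 is "Improvement in eGFR of ≥ 30% compared to Baseline", so the baseline value sets the bar.

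**The concern.** A creatinine drawn, say, 3 days after dialysis ended is rejected after baseline but, on a literal reading, accepted at baseline. Residual lowering of creatinine by dialysis makes eGFR look better than it is. At baseline that raises the value a participant must later reach.

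Baseline eGFR enters the renal component of the primary endpoint, renal response at each visit, time to renal response and change in eGFR. A participant with real recovery could be counted as a nonresponder.

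SAP 9.3.11 ends its rule for platelets and hemoglobin with the same restriction, but there it cannot affect hematologic response: the platelet criterion is an absolute count (at least 150,000/µL). Renal response is relative to baseline, so an error in baseline passes straight into it.

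**Working it through.** **1. The plan's own figure.** The documents give no figure for the size of this effect. The nearest design figure is the approximately 90% power in Protocol 9.2 (2-sided Fisher's exact test, 35% versus 70%). Exact enumeration gives 93.1% at 50 per arm and 88.3% at 45 per arm (50 less 10% dropout). The stated power reproduces, and this point does not affect it.

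**2. What the scope sentence restricts.** It could be read as covering only the sentence just before it, on being dialysis free for 14 days. That is the weaker reading. The 14-day sentence is already limited to post-Baseline time points, so the restriction would add nothing. The scope sentence also names creatinine and eGFR, the subjects of the exclusion and imputation. And SAP 9.3.11 uses the same closing sentence for its whole exclusion rule.

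**3. Whether the case can arise.** Inclusion criterion 5c admits participants newly started on dialysis for TMA before Screening, and Screening runs from Day −14 to Day −1. Dialysis can therefore end shortly before Day 1. The notes to the Schedule of Activities also ask for visits on non-dialysis days where possible. Even a participant between sessions on Day 1 is classified correctly only if the term is understood as intended.

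**4. Size.** Above kappa, the SAP's CKD-EPI equation makes eGFR proportional to SCr^(−1.209). If dialysis has lowered creatinine by a fraction f, then:

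- inflation of baseline eGFR = (1 − f)^(−1.209)
- true improvement needed for renal response = 1.30 × (1 − f)^(−1.209)

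The value of f is an assumption, shown over a range. The third and fourth columns take a true eGFR of 10.

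| f | Inflation | Baseline eGFR | Response threshold | True fold-rise needed |
|---|---|---|---|---|
| 0% | 1.00 | 10.0 | 13.0 | 1.30 |
| 10% | 1.14 | 11.4 | 14.8 | 1.48 |
| 20% | 1.31 | 13.1 | 17.0 | 1.70 |
| 30% | 1.54 | 15.4 | 20.0 | 2.00 |
| 40% | 1.85 | 18.5 | 24.1 | 2.41 |
| 50% | 2.31 | 23.1 | 30.1 | 3.01 |
| 60% | 3.03 | 30.3 | 39.4 | 3.94 |

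For scale, a 30% rise in eGFR corresponds to a creatinine fall of 1 − 1.3^(−1/1.209) = 19.5%. A residual dialysis effect of about 20% is therefore as large as the whole response margin.

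**5. Scheduled visits after baseline.** There is no Day 0. If dialysis ends on Day −1, the fifth day after is Day 5. The first post-baseline laboratory visit is Day 8 ± 2, so Day 6 at the earliest. No scheduled visit falls inside the window for dialysis that ended before Day 1.

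**6. Scale in this study.** SAP 4 reports 16 participants enrolled. Assuming 8 per arm, one reclassified participant moves an arm's response rate by 1/8 = 12.5 points. How many are affected is not stated. Protocol 4.2.2 cites dialysis at presentation in up to 40% or more. If 5% to 15% of those stopped in the relevant 5 days (an assumption), 40% × 5% to 15% is 2% to 6%, or 0.3 to 1.0 of 16 participants.

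**The case against.** The strongest objection is that SAP 9.3.10 contains both a definition and a rule, and that only the rule is restricted. It is the only place in the SAP that says when a participant counts as on dialysis. If that definition carries over to SAP 5.1, a participant within 5 days of stopping is on dialysis at Day 1 and already receives 10. This reading is possible. It is weaker than the literal one, because the scope sentence follows the definition and SAP 5.1 does not refer to it. It would, however, fit the reason given in the Amendment 2 summary for revising baseline eGFR, which was to account for dialysis at baseline. The objection shows that the text needs settling, not that it is settled.

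The second objection is that imputing 10 has its own error, and this stands. Someone who stopped dialysis may be recovering. If true baseline eGFR is 23 and is set to 10, the threshold is 13. An unchanged 23 then scores as (23 − 10)/10 = +130%, and a fall to 13, which is (23 − 13)/23 = 43%, still counts as renal response. The documents do not show which error is larger.

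Third, creatinine may rebound within days of the last dialysis, so some participants may be little affected. This also stands.

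**Conclusion.** The point holds as an inconsistency in the baseline definition. As written, a creatinine value that the SAP would reject after baseline can set the denominator of the 30% renal criterion. If creatinine is still lowered by 20% to 50%, baseline eGFR is inflated 1.31- to 2.31-fold, and the true improvement needed rises from 1.30-fold to between 1.70- and 3.01-fold. The size of the reduction and the number affected are assumptions; possibly no one among the 16 is affected.

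A reader might infer three stronger things that the documents do not support:

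- **A false early fall in eGFR, because the same participant is imputed as 10 days later.** By the day count above, this cannot happen at a scheduled visit held in its window; only an unscheduled sample by Day 5 could be caught. The harm is the inflated baseline itself.
- **A biased treatment comparison.** The error works against response in either arm and would distort a contrast only if affected participants were unevenly split. SAP 4.2 plans no hypothesis test or inferential comparison.
- **That 10 is the correct baseline for these participants.** It is a convention that can err the other way.

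What remains at stake is the descriptive response rates with their confidence intervals, time to renal and Complete TMA Response, and change in eGFR.

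**What to change.** Use one definition of on dialysis for baseline and post-baseline eGFR, settled before treatment assignments are known.

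- **SAP 5.1:** state that baseline eGFR is set to 10 mL/min/1.73 m² if the participant is on dialysis at Day 1, or if the baseline creatinine was obtained within 5 days after the end of dialysis. Refer to 9.3.10 for the definition, and use one term where the section now has both at Baseline and at Day 1.
- **SAP 9.3.10:** replace the last sentence so that the creatinine exclusion and eGFR imputation also cover baseline. The 14-day dialysis-free definition can stay post-baseline.
- **Outputs:** list the participants whose baseline depends on this choice, with the end date of dialysis, the sample date and the measured value. Report Complete TMA Response, renal response and change in eGFR with both the imputed and the measured baseline, so that errors in either direction are visible.

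The cost is a sentence in each of two SAP sections, one listing and one repeated set of summaries. No new data should be needed: Protocol 8.2.2 has dialysis status recorded on the CRF from 14 days before Screening onward, and the existing 5-day window and the duration-of-dialysis endpoint already require dialysis dates. If no participant falls in the window, one sentence in the report saying so closes the matter.
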